## **F) Weekly Phone Assessment**

After the TREATMENT PHASE, the study coordinator will conduct weekly phone contacts with the subjects to ensure their compliance with filling out the headache diary and to assess any side effect until the completion of the study. The study coordinator will also trouble shoot any potential issues that may lead to unnecessary subject dropout with the assistance of the PI.

## **G) Side Effect Assessment**

During each study related visit and weekly phone assessments, side effect assessments will be conducted to monitor any study related complication. Patient will be asked to report any potential neurological side effect related to the study treatment. Investigators will determine whether these side effects are study or non-study related and report the findings to the Institutional Human Subject Protection Committee, VA Research and Development Committee

and the study Data Safety Monitoring Board according to the protocol. If necessary, severe adverse events such as death, suicide, or other life-threatening events or issues will be reported immediately to the HRPP for expedited reporting.

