**C) Other study associated assessments consist of:**

**1) Weekly Phone Assessment:** After the post-treatment one-week assessment, the study coordinator will conduct weekly phone contacts with the subjects for pain and side effect assessments until the completion of the study. The study coordinator will also trouble shoot any potential issues that may lead to unnecessary subject dropout with the assistance of the PI;

**2) Side Effect Assessment:** During each study related visit (after Visit 2) and weekly phone assessment, side effect assessment will be conducted to monitor any study related complication. Patient will be asked to report any

potential neurological side effect such as soreness at the side of the treatment, dizziness, or increase of pain related to the treatment. Investigators will determine whether these side effects are study or non-study related and report to the Institutional Human Subject Protection Committee, VA Research and Development Committee and the study Data Safety Monitoring Board according to the protocol; and

3) **Concomitant Medication:** Any medication that a subject uses during the study is considered concomitant medication. This includes prescription and non-prescription treatment such as contraceptives, vitamins, topical preparations, herbal preparations, and non-pharmacological therapies. Concomitant medication information (please see Human Subject for allowable and prohibited concomitant medications during the study) will be collected for all subjects during the screening, treatment, between visits (recorded in the Daily Headache Log) and subsequent post treatment visits. Information regarding subjects' previous failed treatments will also be collected at the screening visit. Subjects will be instructed not to alter medication regimens during the study without consultation with the investigators.

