## Section 14 - Potential Risks

### 14) Describe any potential or known risks or discomforts and assess their likelihood and seriousness (see ? for guidance)

Risks associated with Repetitive Transcranial Magnetic Stimulation (rTMS) are minimal. A potential side effect of rTMS is a mild headache or headache increase, resulting from muscle stimulation on the scalp. Typically, the headache will resolve spontaneously a few hours after the treatment or with a dose of acetaminophen. Occasionally, skin irritation can occur. This occurrence will be dealt with conservatively. Noise during treatment may also be a concern. However, all subjects will be required to wear earplugs during the treatment session. Some patients may experience sleep disturbance during the course of rTMS or a feeling of increase /decrease of energy level. Although seizure occurrence was reported in the past, to the best knowledge of the investigators, no seizure occurrence has been reported with treatment setting similar to the proposed treatment protocol since the introduction of standard treatment guideline in 1998. These and other risks of the intervention will be fully discussed with the subjects prior to the study and side effect will be assessed during the study as well. Since the MRI scan room consists of strong magnetic field, instruction will be given to each subject prior to entering the scan room so that no subjects with any metal denture, implanted metal device such as aneurysm clips, cardiac pacer or spinal fusion rods will be allowed to enter the scan room. A screening survey will be conducted as required by the MRI center. The magnet of scanner may cause dizziness, which can be avoided with slow movement when the subjects are near the scanner. These and other risks of the intervention will be fully discussed with the subjects prior to the study and side effects will be assessed during the study as well.

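### The side-effect question put to patients is narrower than the plan's own stated scope and risk list, and asks patients to screen for relatedness before the blinded investigators do

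*Combined protocol and SAP*

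**What the plan says.** Two places describe what patients are asked. Section 9, G) states: "Patient will be asked to report any potential neurological side effect related to the study treatment". Section 9, C) item 2 asks for any "potential neurological side effect such as soreness at the side of the treatment, dizziness, or increase of pain related to the treatment". In C) the closing relatedness phrase could belong to the whole list or only to increased pain; in G) it plainly governs the whole question.

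Other parts of the plan set a wider scope:

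- The opening sentence of G) says "side effect assessments will be conducted to monitor any study related complication", and C) item 2 opens to the same effect.
- F) Weekly Phone Assessment says the calls are "to assess any side effect until the completion of the study", with no limit to neurological or treatment-related effects.
- Section 14 lists rTMS risks beyond headache and seizure: "Occasionally, skin irritation can occur"; "Noise during treatment may also be a concern"; "Some patients may experience sleep disturbance during the course of rTMS"; and a change in energy level. It adds that side effects will be assessed during the study.

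On causality, G) says "Investigators will determine whether these side effects are study or non-study related". The Blinding Strategy and Assessment section keeps both the coordinator and the investigators blind to allocation.

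**The concern.** The wording of the question determines what enters the harms record. If staff follow the text as written, they ask about a narrower class of event than the plan says it wants to monitor, and than it warns of in Section 14. They also ask the patient to make a first judgement of cause. The investigators can classify an event as unrelated, but only if they hear of it.

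Two things are at stake. The first is completeness: an event type that is not prompted is recorded only if it is volunteered or noticed. The second is comparability between arms: what a patient attributes to rTMS may depend on which treatment the patient believes was given. The plan takes that belief seriously enough to survey it at Visits 5, 8 and 14. Section 17 presents rTMS as a low-risk treatment, and that description rests on the harms record. Events missed at the time cannot be reliably recovered later.

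**Working it through.** The plan gives no figure on this point, so the check is a comparison of the passages.

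**1. Scope of each text**

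| Place | Contacts covered | Neurological only? | Related to treatment only? |
|---|---|---|---|
| C) item 2, aim | Visits after Visit 2; weekly calls | No | Yes |
| C) item 2, question | Same | Yes | At least for increased pain |
| F), calls | Weekly calls after the treatment phase | No | No |
| G), aim | Study visits; weekly calls | No | Yes |
| G), question | Same | Yes | Yes |
| Section 14, general statement | During the study | No | Refers to risks of the intervention |

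In both C) and G) the question is narrower than the aim stated just before it. G) also covers the weekly calls, so on those calls it conflicts with F).

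**2. Section 14 risks against the two questions**

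- Headache or increased headache: covered by the pain example in C).
- Skin irritation: not named, and not neurological.
- Noise: not named; a complaint about it is not obviously neurological.
- Sleep disturbance: not named; a patient may not connect it with treatment.
- Change in energy level: not named, for the same reason.

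**3. Which wording applies during treatment**

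The weekly calls begin after the treatment phase according to F), or after the one-week post-treatment assessment according to C) item 1. Either way, they do not reach Visits 3-12. At those ten sessions, when skin or noise complaints would be most likely, C) item 2 and G) are the only descriptions of what is asked.

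**4. Order of the relatedness judgement**

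The patient is asked for effects related to treatment, and the investigators then sort the answers into study-related and not. The second category can be filled only by events that passed the patient's own screen.

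**5. Whether the bias can be sized**

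Let p be the true event rate, taken as equal in both arms, and let a(A) and a(B) be the proportions of active and sham patients who link an event to treatment. If the relatedness filter were applied strictly, the recorded rates would be p × a(A) and p × a(B), with ratio a(A)/a(B). That ratio is 1 when attribution is equal, departs from 1 otherwise, and does not depend on p. The documents give neither a(A) nor a(B), so any figure would only restate an assumption.

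**The case against.** A reader might infer that side effects are elicited only when neurological and treatment-related, so that the listed risks are never asked about. The documents do not support that. F) covers any side effect, the aims in C) and G) carry no neurological limit, and Section 14 promises assessment in general terms. The examples in C) include local soreness, so the word neurological is used loosely. The fault is inconsistency, not uniform exclusion.

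A reader might also infer that patients' attribution decides what counts as a harm. It does not: patients report potential effects, and blinded investigators make the classification. Serious events have separate routes, through immediate reporting of life-threatening events under G) and DSMB review under Section 9.9.

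There is partial cover elsewhere:

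- The Hamilton scale includes insomnia, the SF-36 includes vitality, and the NSI rates symptom disturbance, all without asking for attribution.
- The diary records headache daily.
- Section 15 has procedures performed or supervised by clinicians and plans for managing skin irritation.
- Earplugs are required.

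The sham coil imitates sound and scalp sensation, which should limit differences in perceived allocation. No hypothesis includes a harms endpoint. Finally, these passages summarise a procedure; the actual form or script is not among the documents and may be broader.

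Much of this stands, and it limits the claim. It does not remove the point. The scales are outcomes collected before and after treatment, not harms recorded session by session. A plan to manage skin irritation is not a prompt to report it. Section 14 says that side effects will be assessed without saying how, and the passages that do say how are the narrow ones. No open question or checklist is described.

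**Conclusion.** The point holds as a wording inconsistency with a practical consequence. The patient question in C) item 2 and G) is narrower than the plan's stated scope and its Section 14 risk list. It also invites patients to screen for relatedness before the blinded investigators do. Events that a patient does not link to rTMS may therefore not be recorded, particularly at Visits 3-12.

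This rests on the assumption that staff follow the question as written and that no unseen form broadens it. The number of events lost and any resulting bias between arms cannot be determined from the documents. A particular ratio of recorded harms, however tempting as an illustration, would have no basis in them. The primary efficacy analysis is unaffected. The change is worth making because it is cheap and improves harms capture.

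**What to change.** Reconcile C) item 2, F) and G) into one procedure, used at the contacts already planned and identically in both arms:

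1. Ask an open question about any new or worsened problem since the last contact, whatever its cause.
2. Follow it with brief prompts for each risk named in Section 14, including skin irritation, noise, sleep and energy change.
3. Record every answer, and have the blinded investigators judge relatedness afterwards.
4. Tabulate events by arm, both overall and by relatedness.

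In the same edit, settle when the weekly calls start, since C) item 1 and F) differ. If an existing form already does this, align the protocol text with it.

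The cost is a revision of the script and case-report form, a few more minutes per contact, and more unrelated events to record. Treatment, visits and sample size do not change.

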## **Data Management, Analysis and Power Calculations:**

Missing data values will be minimized by intensive training of the staff involved in the study. Missing data will be examined to assess randomness and the pattern of missing data according to the procedure recommended by Little and Rubin [47]. The investigators will test whether the dropouts are random or systematic by comparing the dropouts with the study completers on the baseline data. An absence of significant differences would support the random nature of dropouts.

Initially, descriptive statistics and exploratory graphing such as frequencies, means, standard deviations, box and whisker plots, stem and leaf diagrams, and scatter plots will be used to assess the normality of the data in terms of the presence of skew and/or outliers. The continuous outcome data will be transformed if necessary by using an appropriate transformation such as the log transform for skewed long tailed data. Similarly, potential covariates will also be summarized with descriptive statistics and graphs to determine the most appropriate way to treat these variables and to decide if a continuous, categorical, or an interval representation is the most appropriate approach.

Data acquired in this project will be managed and analyzed by the study statistician, [name]. Customized database system will be developed for this project to ensure the highest possible data reliability by the study biostatistician. The system will include but is not restricted to: (i) patient demographic input and query; (ii) patient recruitment, scheduling and protocol tracking; (iii) data storage, compilation, selection, and summary transfer to various statistical and graphical sub-systems; (iv) administrative document and report management and, (v) data backup and archival control. Data entry programs will include item prompts, skip patterns, range checks, and logical validity routines. Standard data security protocol will be used for this project. These include, but are not limited to: assigning a unique ID number for each subject, storing confidential information in an encrypted form, using VA secure server, limiting accessibility of data to authorized Center personnel. An electronic archive of all data is kept offsite to insure against loss by fire, theft, etc. All statistical transfer routines are inherently secure via their operating platform and they contain no patient names or personal data.

For hypotheses 1 and 2, where multiple analyses are conducted, correction for family-wise Type I error rates will be made using the Westfall-Young randomization maxTprocedure, which adjusts p-values for significance while taking into account the correlation of the outcomes [76]. In this way, the study can control for an overall family-wise error rate of .05 while achieving more power than Bonferroni adjustments. Using this method of power analysis, the investigators estimated a sample size of 128 (64 per group, accounted for a 20% dropout rate) provides the study with 85% power

to detect a medium effect size (RMASS program provided by Hedeker) [25; 26]. Medium effect sizes were used based on the results included in the above sections. Medium effect size is defined as a between-group difference increasing linearly from 0 at baseline to .5 SD units at the last time point. The minimum power estimation is based on sample size calculation for 10% and 20% attrition, correlations of 0.2, 0.5, and 0.8 between the repeated measures, and for medium and large effect sizes. Data will be analyzed using SPSS version 23, all analyses will be two-tailed, where applicable with  $\alpha = .05$ .

**Hypothesis #1:** Active rTMS at LMC provides significantly more reduction in headache intensity, duration and frequency of exacerbation than sham rTMS.

Independent Variables: Treatment Groups with two levels (Groups A & B), Visits up to 8 (See below). Dependent Variables: Primary outcome: Average daily headache assessments (B1, B2, B3, B4, B5, B6); Secondary outcome: Debilitating Headache Composite Score (B1, B2, B3, B4, B5, B6); M-VAS Scores of headache (Visits 2, 7, 12, 13, 14, 15, 16, 17); HTL-6 and NSI (Visits 2,13,14,15, 16, 17); headache rescue medication usage (Visits 2,13, 14, 15,16, 17). Note, not all variables are collected at all visits.

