#### Research Design:

A total of 200 will be consented and 128 (64 per group, accounted for 36% dropout rate) patients will be randomized to be stratified based on their injury mechanisms (blast, non-blast) and headache severities (mild, moderate, severe) and enrolled over 6 years from VASDHS, and Naval Medical Center San Diego (MNCS). Patients meeting study enrollment criteria will be randomized into one of the two study groups (A&B) based on their mechanisms of injury, gender, severity of headache, and past failed therapies for their headache. The overall study duration for each subject is about 14 weeks developed into three phases according to the following schedule:

- 1) PRE-TREATMENT PHASE (weeks 1-2) consists of Visit 1 (Screening Visit) and Visit 2 (Pre-treatment Assessments);
- 2) TREATMENT PHASE (week 3-4) consists of Visits 3-12 (Neuronavigation guided rTMS consisting of 10 weekday treatments at  $>24$  and  $< 72$  hours apart, weekends excluded, maximum 5 weeks for treatment completion) rTMS will take place in Building 23 Room 105 at the VASDHS; and

3) POST-TREATMENT PHASE (week 5-14) consists of two initial weekly visits (Visits 13&14) and two additional biweekly visits (Visits 15&16) and one monthly visit (Visit 17).

Brain anatomical and functional MRI will be performed within 72 hours after Visits 2 and 13. Subjects will be required to fill out headache diary between assessment visits. Headache assessments along with quality of life, mood and functions assessments will be carried out at Visits 1,2, and 13--17. This frequency of treatment and duration of follow-up is in line with recently published rTMS articles related to TBI, headache and pain, and also in accordance with the 3-month post treatment initiation follow-up guideline /recommendation [32; 55; 80].

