### **Statistical Analysis:**

Data will be analyzed using mixed effects model [12; 27; 35]. This approach provides more information and therefore, more power compared to cross-sectional analyses, which focus on the analysis of one summary index, or more traditional analytic approaches such as a change score, end-point or repeated measures analysis of variance. In this approach, the repeated measures over time for each individual subject form a trajectory that can be described by a relatively simple model with a few parameters, such as intercept (baseline value) and slope (rate of change). With repeated measures, repeated observations within subjects are potentially correlated for any impact on the resulting tests of significance [34]. When this within subject correlation is properly incorporated, the repeated measures analysis takes full advantage of all information obtained from each subject, thereby greatly increasing the statistical power over methods that compare treatments cross-sectionally [23]. This approach can model for the differential patterns over the repeated assessments, instead of the totals at one point. As a result, this analytical approach increases the reliability of the measurement of response (since the slope combines repeated measures, which cancel much of the error of measurement), and will increase the protection against the major effects of missing data. In addition, the influence of missing data is reduced since it maximizes the number of subjects by allowing the inclusion of subjects with missing data, dropouts or those who are terminated early in the study without relying on data imputation procedures. The investigators will use pattern-mixture models to assess if there is any bias due to drop out or missing data. These will result in

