increased power to detect effects and precision for the estimation of the effect sizes without requiring increased sample size, and provide the study with a uniform method of data analysis for all hypotheses that include multiple measurements from the same subjects. The mixed effects model method provides an estimate of the individual variability around the population trend, the variability of the individual intercepts (baseline values) and slopes (changes across time), and the correlation between them. A fully saturated treatment by time model will be utilized for inference. Co-variance structure will be chosen based on Akaike's Information Criterion (AIC). This allows for any group level effects to be incorporated into the model. Denominator degrees of freedom will be calculated using the Kenward-Roger small sample correction. Analyses will be conducted within and across nested levels of the study design; this will involve within-subject analyses (comparison of occasions of measurement nested within an individual), as well as between-subject analyses (comparison of two groups). In addition, any treatment group comparison can be adjusted for subject-specific characteristics and adjustments for changes in these characteristics over the course of the study, and incorporated into the single-subject analyses. Based on investigators' experience with previously completed studies, we expect a dropout rate of 10 to 20% throughout the study. All analyses will be two-tailed, where applicable, with  $\alpha = .05$ . Correction for family-wise Type I error rates will be made using the Westfall-Young randomization maxT procedure, which adjusts p-values for significance while taking into account the correlation of the outcomes [70]. In this way we can control for an overall family-wise error rate of .05 while achieving more power than Bonferroni adjustments.

**Hypothesis #2:** Active rTMS at LMC provides significantly more improvement in quality of life, mood and functions than sham LMC stimulations.

Independent Variables: Treatment Groups with two levels (Groups A & B), Visits with 8 levels: pre-treatment (Visit 2), treatment (Visits 7 & 12), and Post-treatment (Visits 13, 14, 15, 16, 17).

Dependent Variables: Attention (CPT II), Memory (Hopkins Verbal Learning Test) Execute function (Trail Making Test A and B, and Stroop Test), Hamilton Depression Scale, SF-36 and BPI.

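### A non-significant baseline comparison of dropouts with completers cannot support random dropout; the inference should go, and the planned pattern-mixture analysis should be made concrete

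*Combined protocol and SAP*

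**What the plan says.** Three statements in Section 9 bear on this point.

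- **The check.** Under Data Management, Analysis and Power Calculations, "Missing data will be examined to assess randomness and the pattern of missing data", with a reference to a published procedure. The text continues: "The investigators will test whether the dropouts are random or systematic by comparing the dropouts with the study completers on the baseline data".
- **The inference.** The next sentence reads: "An absence of significant differences would support the random nature of dropouts". No power, equivalence margin, post-baseline variable or by-arm comparison accompanies it.
- **The analysis and its safeguard.** The Statistical Analysis text for Hypothesis #1 uses a mixed effects model on all available data without imputation, and adds: "The investigators will use pattern-mixture models to assess if there is any bias due to drop out or missing data". The patterns, identifying restrictions and any sensitivity parameter are not given.

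On the amount of dropout, the same Statistical Analysis text says "we expect a dropout rate of 10 to 20% throughout the study". The power paragraph also uses 20%.

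**The concern.** The sentence treats failure to reject as evidence of no difference, in a comparison where one group will be small. It also looks only at baseline. In a sham-controlled trial an obvious reason to leave is lack of benefit, and that arises after baseline. The protocol's own background (Section 7) reports at least 50% headache reduction in 80% of active and 20% of sham patients in the earlier trial, so leaving for lack of benefit could differ by arm.

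At stake is what the trial may claim. A null baseline comparison could be reported as grounds for calling dropout random, and hence for trusting an analysis that assumes missing at random, when the comparison gives little support for either. It is also the only place in the plan that says what a missing-data result would mean.

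**Working it through.** **The plan's own figure.** The documents give no power for the dropout comparison, so there is nothing to reproduce. The stated 85% power belongs to the main treatment comparison and is not needed here.

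**Inputs.** N = 128 (power paragraph); dropout 10 to 20% (Statistical Analysis); two-sided alpha 0.05 (power paragraph); planned effect "a between-group difference increasing linearly from 0 at baseline to .5 SD units at the last time point".

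**Step 1: group sizes.**
- 10%: 0.10 × 128 = 12.8, so 13 dropouts v 115 completers.
- 20%: 0.20 × 128 = 25.6, so 26 v 102.

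**Step 2: power of a two-sample t test on one baseline variable.** The noncentrality is d × √(n1 × n2 / (n1 + n2)), with n1 + n2 − 2 = 126 degrees of freedom.
- 13 v 115: √(13 × 115 / 128) = 3.418. For d = 0.5 the noncentrality is 1.709.
- 26 v 102: √(26 × 102 / 128) = 4.552. For d = 0.5 the noncentrality is 2.276.

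| Dropout | Groups | 0.3 SD | 0.5 SD | 0.8 SD |
|---|---|---|---|---|
| 10% | 13 v 115 | 17% | 40% | 77% |
| 20% | 26 v 102 | 27% | 62% | 95% |

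A 0.5 SD baseline difference would be missed 38 to 60% of the time.

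Research Design attaches a different rate to the same 128: "128 (64 per group, accounted for 36% dropout rate) patients will be randomized". Since 200 × 0.64 = 128, this looks like loss between consent and randomization. Read as post-randomization dropout it gives 46 v 82 and 77% power for 0.5 SD.

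**Step 3: what a baseline test can see.** Dropout was simulated with one baseline and one final measurement, normal outcomes, and an assumed odds ratio of 2 per SD of response (2,000 replicates per scenario).
- Dropout driven by the part of response independent of baseline: at baseline–final correlation 0.5, the baseline test rejects in 4.7 to 5.8% of trials at 10, 20 and 36% dropout. That is its false-positive rate.
- Dropout driven by final level or raw change, both correlated with baseline: it rejects in 7 to 43% (10% dropout) and 9 to 66% (20% dropout), depending on the correlation. In these same-direction scenarios the baseline-adjusted completer estimate of a true 0.50 SD effect stays at about 0.47 to 0.50 SD.
- Poor responders leaving sham and good responders leaving active, 20% dropout, correlation 0.5: the test rejects in 5%, while a baseline-adjusted completer analysis shrinks 0.50 SD to about 0.28 SD. That is a completer analysis, not the planned mixed model.

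**Step 4: illustrative effect on the estimate.** If a fraction f of one arm drops out and their unobserved mean differs by δ from what the model implies, the arm mean at the last time point shifts by f × δ.
- f = 0.20, δ = 0.5 SD: 0.10 SD, or 0.10 / 0.5 = 20% of the planned effect.
- f = 0.20, δ = 1 SD: 0.20 SD, or 0.20 / 0.5 = 40%.

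Equal f and δ in both arms would cancel.

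**The case against.** The case for the plan is substantial, and most of it stands.

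- **The safeguard is unconditional.** A reader might infer that a null baseline test would settle the question and displace the pattern-mixture models. Nothing in Section 9 makes them depend on that test.
- **Dropout that differs by arm does not by itself bias the primary estimate.** A reader might infer that it does. A correctly specified likelihood-based mixed model on all available data stays valid when dropout depends on observed responses, even if it differs by arm. Headache is recorded daily in the diary, so leaving after a recorded lack of benefit is largely covered.
- **The sentence triggers no action.** It selects no model and cancels no analysis; it is an interpretation.
- **Pooling of the arms is not stated.** The text does not say whether the comparison is pooled or by arm.
- **The check is not wholly blind or always weak.** It has incidental power when the response driving dropout correlates with baseline, and 95% power for 0.8 SD at 20% dropout. Several baseline variables would be compared, so the whole check would flag a difference more often than one test, though also more often by chance.
- **The shift in Step 4 is not caused by the sentence.** It would be the same if the sentence were deleted. It shows what is at risk if the inference is believed.

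None of this makes the inference valid. It narrows the consequence.

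**Conclusion.** The sentence is a genuine error of inference and should not stand. At the planned dropout, one baseline test has 40 to 62% power for a 0.5 SD difference, and no baseline test can detect dropout driven by the part of response independent of baseline.

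The documents do not support the stronger conclusions that the sentence overrides the pattern-mixture models, or that arm-dependent dropout alone invalidates the primary estimate. The remaining threat is dropout driven by unobserved response. The only planned protection against it is a pattern-mixture analysis without stated patterns, restrictions or sensitivity parameter.

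The 0.1 to 0.2 SD shift rests on an assumed departure of 0.5 to 1 SD confined to one arm with 20% dropout. The documents supply no value for that departure. The simulation rests on the assumed odds ratio and normal outcomes. Replacement patients, allowed for under the randomization process, are not modelled and could change the dropout counts.

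**What to change.** 1. Delete the sentence, and state that the baseline comparison will not be used to judge whether dropout is ignorable.
2. Describe dropout by arm, timing, reason and last diary score. This is descriptive only: within one arm at 20% dropout the groups are about 13 v 51, with 35% power for 0.5 SD, and observed scores cannot establish missing at random.
3. Specify the planned pattern-mixture analysis of the primary outcome as a delta-adjusted tipping-point analysis. Let delta vary separately by arm, fix its range before unblinding, and report it whatever any test shows. This is the essential part.

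The cost is SAP wording and a small amount of extra analysis. The diary data are already collected, and neither sample size nor conduct changes.
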